## 2.5 Rationale

Malignancies were one of the earliest recognized manifestations that lead to the eventual description of the acquired immune deficiency syndrome (AIDS) epidemic. Kaposi sarcoma (KS) became one of the first entities described in association with AIDS (Ziegler, Templeton, and Vogel, 1984). Subsequently, intermediate-grade and high-grade non-Hodgkin's lymphoma (NHL), invasive cervical cancer and primary central nervous system lymphoma (PCNSL) were defined by the Centers for Disease Control and Prevention (CDC) as "AIDS-defining" conditions (CDC, 2008).

The introduction of combination active anti-retroviral therapy (cART) in the 1990s has enormously impacted the outcomes of HIV infection. In addition to changing the natural history of HIV infection, in terms of survival and incidence of opportunistic diseases, it has also dramatically decreased the incidence of some virally mediated HIV-associated malignancies, such as KS or PCNSL. However, several other cancers that are not AIDS-defining have been found to have increased incidence in patients with HIV, and therefore are considered AIDS-associated malignancies. These include Hodgkin's disease, melanoma, anal, vaginal, liver, lung, oropharyngeal, leukemia, colorectal and renal cancer (Patel, Hanson, *et al.*, 2008).

Management of malignancies in patients with HIV infection presents the clinician with many challenges. These include the risk of further immunocompromise with chemotherapy; toxicities of treatment; potential of pharmacologic interaction between cART and chemotherapy drugs and the risk of intercurrent opportunistic infections. Thus, careful pharmacokinetic evaluation of potential new biologic targets against both ADMs and NADCs is necessary.

Cabozantinib (XL184) is small molecule potent inhibitor of multiple receptor tyrosine kinases (RTKs) implicated in tumor growth, metastasis, and angiogenesis. The agent is a potent inhibitor of MET and VEGFR2, with half-maximal inhibitory concentration (IC50) values of 1.3 nmol/L and 0.035 nmol/L, respectively (Yakes *et al.*, 2011). Cabozantinib strongly inhibits several other kinases that have also been implicated in tumor pathobiology, including KIT, RET, AXL, TIE2, and FLT3 (IC50 = 4.6, 5.2, 7, 14.3, and 11.3 nmol/L, respectively).

The RTK pathways inhibited by cabozantinib may apply to broad patient settings. c-MET is the receptor for the hepatocyte growth factor (HGF) with tyrosine kinase activity, and its activation has been implicated in tumor cell migration, invasion, proliferation and angiogenesis (Eder *et al.*, 2009). VEGFR2 is the predominant mediator of VEGF-stimulated endothelial cell migration, proliferation, survival, and enhanced vascular permeability (Roskoski, 2008). In early-phase clinical trials, cabozantinib (XL184) monotherapy was associated with partial responses in patients with glioblastoma, medullary thyroid cancer (Kurzrock *et al.*, 2011), castrate-resistant prostate cancer, non-small cell lung cancer, ovarian cancer, breast cancer, and hepatocellular carcinoma. Cabozantinib is under phase III investigation for medullary thyroid cancer, with recently reported top line data indicating that the primary endpoint of the study, progression-free survival (PFS) was met. PFS on the cabozantinib arm was 11.2 months compared to 4.0 months on placebo, hazard ratio [HR] 0.28, p < 0.0001 (Schoffski *et al.*, 2012). As of March 1, 2011, the most frequently (>20%) observed adverse events (AEs) in 806

patients treated in single agent, open label cabozantinib studies, regardless of the relationship to cabozantinib, were fatigue, diarrhea, nausea, decreased appetite, constipation, palmar-plantar erythrodysesthesia (PPE) syndrome, vomiting, dysphonia and hypertension. Effects that may be related to the inhibition of VEGF, including hypertension, thromboembolic events, GI perforation, fistula formation, hemorrhage, wound healing complications, and proteinuria, have also been observed (Investigator's Brochure, 2012).

We now propose a phase I, dose escalation trial of cabozantinib in persons with HIV infection with advanced solid tumors. Given the broad range of anticancer activity observed in early phase studies, access to and evaluations of tolerability of this agent in persons with HIV infection is warranted so that such patients may be included on phase III trials of this agent. Certainly, effects on HIV/AIDS associated Kaposi sarcoma (example of a rare tumor) and hepatocellular carcinoma and non-small cell lung cancer (more common in persons with HIV-infection) would be of great clinical interest due to cabozantinib's effects on MET and VEGFR. Overexpression of HGF may have a role in angiogenesis of Kaposi sarcoma lesions (Naidu *et al.*, 1994) and evidence of VEGF/VEGFR2 and HGF/c-MET autocrine loop induction has been observed (Masood *et al.*, 1997; Maier *et al.*, 1996). *MET* mutations have been observed in gastric and liver cancer, small cell and non-small cell lung cancer, and metastases of head and neck squamous cell carcinoma, and gene amplifications in *c-MET* have also been observed in 15-25% of these tumors (Christensen *et al.*, 2005).

## 2.6 Correlative Studies Background

2.6.1 To investigate possible pharmacokinetic interactions between cabozantinib and antiretroviral therapy in persons with HIV infection.

This study will enroll subjects with HIV infection across three Strata based on current antiretroviral regimen CYP3A4 inhibitor (Ritonavir or Cobicistat)-containing HAART [**Stratum A**]; CYP3A4 inducer (Efavirenz or Etravirine)-containing HAART [**Stratum B**]; and Others [**Stratum C**]): with designation of HAART Stratum effective November 30, 2012. Subjects who are not taking a HAART regimen and are eligible for study will be included in Stratum C. The study therefore provides an opportunity to evaluate possible pharmacokinetic interactions between cabozantinib and antiretroviral therapies.

There are data suggesting that cabozantinib: 1) is a CYP3A4 substrate, 2) is unlikely to induce or inhibit CYP450 enzymes in patients, and 3) inhibits but is not a substrate of ABCB1. Given potential for drug-drug interactions with antiretroviral agents, pharmacokinetic (PK) sampling studies are proposed for all participating patients. Evaluations will occur at steady-state (Cycle 1, Days 22/23) given the long half-life of the drug ( $91.3\pm33.3$ hr) which is not conducive to a comprehensive assessment after a single dose.

2.6.2 To investigate the effects of therapy on patient immune status and HIV viral load.

This trial will include patients with HIV infection, provided patients are receiving appropriate treatment and followed by physicians monitoring their care. While it is not anticipated that cabozantinib will alter immune reconstitution in patients

due to either a drug-drug interaction with the antiretrovirals or a pharmacodynamic effect, HIV viral load and CD4+ and CD8+ cell counts will be monitored to ensure adequate control of the patient's HIV infection.

2.6.3 To preliminarily assess objective response rates associated with treatment for commonly represented tumors.

Although not a traditional role for a phase I trial, this study provides an opportunity to preliminarily identify a signal of clinical activity of cabozantinib for particular malignancies in the setting of HIV infection. Cabozantinib as a single agent has known single agent activity in liver and lung cancers, and given excess frequency of these diseases in HIV it is expected that subjects with these diseases will participate. Other frequent malignancies in persons with HIV infection include head and neck cancers, anal cancer, and Kaposi sarcoma, for which data with cabozantinib is currently limited. We propose to evaluate response outcomes in study participants and report response rates for single agent cabozantinib in commonly represented malignancies.

### **3.0 PARTICIPANT SELECTION**

#### **3.1 Eligibility Criteria**

3.1.1 Participants must have known HIV infection (see [Section 3.1.3](#)) and histologically confirmed solid malignancy that is metastatic or unresectable and for which standard curative or palliative measures do not exist or are no longer effective.

Any number of prior cancer therapies will be permitted. At least 4 weeks must have elapsed since prior chemotherapy or biological therapy, 6 weeks if the regimen included BCNU or mitomycin C. Prior radiation therapy to the thoracic cavity, abdomen, or pelvis must be completed at least 3 months prior to registration; radiotherapy to any other site (including bone or brain metastases) must be completed at least 28 days prior to registration.

3.1.2 Age  $\geq 18$  years on day of consent.

children are excluded from this study.

3.1.3 Serologic documentation of HIV infection at any time prior to study entry, as evidenced by positive ELISA, positive Western blot, or any other federally approved licensed HIV test. Alternatively, this documentation may include a record that another physician has documented that the participant has HIV infection based on prior ELISA and Western blot, or other approved diagnostic tests.

3.1.4 ECOG performance status  $\leq 2$  (Karnofsky  $\geq 60\%$ , see [Appendix II](#)).

3.1.5 Life expectancy of greater than 12 weeks.

3.1.6 Participants must have normal organ and marrow function as defined below within 1 week of study entry:

Leukocytes	$\geq 3,000/\text{mcL}$
Absolute neutrophil count	$\geq 1,500/\text{mcL}$
Platelets	$\geq 100,000/\text{mcL}$
Total bilirubin	$\leq 1.5 \times \text{ULN}$ (If, however, the participant has Gilbert's disease or unconjugated hyperbilirubinemia that is considered to be secondary to atazanavir or indinavir therapy, then the total bilirubin must be $\leq 3 \times \text{ULN}$ )
AST(SGOT)/ALT(SGPT)	$\leq 3.0 \times$ institutional upper limit of normal
Creatinine	$\leq 1.5 \times \text{ULN}$
Creatinine clearance	$\geq 50 \text{ mL/min}/1.73 \text{ m}^2$ for participants with creatinine levels above institutional normal.
Hemoglobin	$\geq 9 \text{ g/dL}$

Serum albumin	$\geq 2.8\text{g/dL}$
Lipase	$<2.0 \times \text{ULN}$ and no radiologic or clinical evidence of pancreatitis
Urine protein/creatinine ratio (UPCR)	$\leq 1$
Serum phosphorus, calcium, magnesium, and potassium	$\geq$ lower limit of normal (LLN)

Additionally, a CD4+ lymphocyte count  $> 50/\text{mcL}$  will be required within 2 weeks of study participation.

3.1.7 Women of childbearing potential must have a negative pregnancy test within 7 days before enrollment. Women of childbearing potential include women who have experienced menarche and who have not undergone successful surgical sterilization (hysterectomy, bilateral tubal ligation, or bilateral oophorectomy) or are not postmenopausal. Postmenopause is defined as amenorrhea  $\geq 12$  consecutive months. Note: women who have been amenorrheic for 12 or more months are still considered to be of childbearing potential if the amenorrhea is possibly due to prior chemotherapy, antiestrogens, ovarian suppression or any other reversible reason.

3.1.8 The effects of cabozantinib on the developing human fetus are unknown. For this reason and because tyrosine kinase inhibitors agents as well as other therapeutic agents used in this trial are known to be teratogenic, women of child-bearing potential and men must agree to use adequate contraception (see below) prior to study entry and for the duration of study participation. Should a woman become pregnant or suspect she is pregnant while she or her partner is participating in this study, she should inform her treating physician immediately. Men treated or enrolled on this protocol must also agree to use adequate contraception prior to the study, for the duration of study participation, and 6 months after completion of cabozantinib administration.

Sexually active participants (men and women) must agree to use medically accepted barrier methods of contraception (e.g., male or female condom) during the course of the study and for 6 months after the last dose of study drug(s), even if oral contraceptives are also used. All participants of reproductive potential must agree to use both a barrier method and a second method of birth control during the course of the study and for 6 months after the last dose of study drug.

3.1.9 Participating participants MUST receive appropriate care and treatment for HIV infection, including antiretroviral medications, when clinically indicated and should be under the care of a physician experienced in HIV management. Participants will be eligible regardless of antiretroviral medication (including no antiretroviral medication) provided there is no intention to initiate therapy or the regimen has been stable for at least 4 weeks with no intention to change the regimen within 8 weeks following study entry. As study-specific (antiretroviral-

based) strata fill, however, only participants who are receiving the therapies eligible for the remaining open strata will be accrued.

- 3.1.10 Ability to understand and the willingness to sign a written informed consent document.
- 3.1.11 Participants must in the opinion of the investigator be capable of complying with this protocol.

### 3.2 Exclusion Criteria

- 3.2.1 Prior treatment with cabozantinib (XL184).
- 3.2.2 The participant has received radionuclide treatment within 6 weeks of the first dose of study treatment.
- 3.2.3 The participant has received prior treatment with a small molecule kinase inhibitor or a hormonal therapy (including investigational kinase inhibitors or hormones) within 4 weeks or five half-lives of the compound or active metabolites, whichever is longer, before the first dose of study treatment. Note: Participants with prostate cancer currently receiving LHRH or GnRH agonists may be maintained on these agents.
- 3.2.4 The participant has received any other type of investigational agent within 28 days before the first dose of study treatment.
- 3.2.5 The participant has not recovered to baseline or CTCAE  $\leq$  Grade 1 from toxicity due to all prior therapies except alopecia and other non-clinically significant AEs.
- 3.2.6 The participant has a primary brain tumor.
- 3.2.7 The participant has active brain metastases or epidural disease. Participants with brain metastases previously treated with whole brain radiation or radiosurgery or participants with epidural disease previously treated with radiation or surgery who are asymptomatic and do not require steroid treatment for at least 4 weeks before starting study treatment are eligible. **Participants with treated brain metastasis should not take enzyme-inducing anticonvulsive therapies (EIACDs) within 2 weeks of registration, though non-enzyme inducing anticonvulsive drugs such as levetiracetam are allowed.** Neurosurgical resection of brain metastases or brain biopsy is permitted if completed at least 3 months before starting study treatment. Baseline brain imaging with contrast-enhanced CT or MRI scans for participants with known brain metastases is required to confirm eligibility.
- 3.2.8 The participant has prothrombin time (PT)/International Normalized Ratio (INR) or partial thromboplastin time (PTT) test  $\geq 1.3 \times$  the laboratory ULN within 7 days before the first dose of study treatment.
- 3.2.9 The participant requires concomitant treatment, in therapeutic doses, with anticoagulants such as warfarin or warfarin-related agents, heparin, thrombin or Factor Xa inhibitors, or antiplatelet agents (e.g., clopidogrel). Low dose aspirin ( $\leq 81$  mg/day), low-dose warfarin ( $\leq 1$  mg/day), and prophylactic low molecular weight heparin (LMWH) are permitted.

3.2.10 The participant requires chronic concomitant treatment with the following strong CYP3A4 inducers OTHER than antiretroviral agents: dexamethasone, phenytoin, carbamazepine, rifampin, rifabutin, rifapentine, phenobarbital, primidone, modafinil, and other enzyme inducing anti-convulsant drugs (EIACD), and St. John's Wort. Use of efavirenz or etravirine is permitted for participants considered for the CYP3A4-inducer based ART regimen arm (Stratum B) of the trial.

Because the lists of CYP3A4 inducers are constantly changing, it is important to regularly consult a frequently-updated list such as <http://medicine.iupui.edu/clinpharm/ddis/table.aspx>; medical reference texts such as the Physicians' Desk Reference may also provide this information. As part of the enrollment/informed consent procedures, the participant will be counseled on the risk of interactions with other agents, and what to do if new medications need to be prescribed or if the participant is considering a new over-the-counter medicine or herbal product.

3.2.11 The participant requires concomitant treatment with the following inhibitors of CYP3A4:

- Antibiotics: clarithromycin, erythromycin, telithromycin, troleandomycin
- Antifungals: itraconazole, ketoconazole, voriconazole, fluconazole, posaconazole
- Antidepressants: nefazodone
- Antidiuretic: conivaptan
- GI: cimetidine, aprepitant
- Hepatitis C: boceprevir, telaprevir
- Miscellaneous: Seville oranges, grapefruit, or grapefruit juice and/or pummelos, star fruit, exotic citrus fruits, or grapefruit hybrids). Use of any of anti-retrovirals (delavirdine) or protease inhibitors (ritonavir, indinavir, lopinavir/ritonavir, saquinavir, nelfinavir) is permitted. Specifically, ritonavir and cobicistat is permitted for participants considered for the CYP3A4-inhibitor based ART regimen arm (Stratum A) of the trial.

Because the lists of CYP3A4 inhibitors are constantly changing, it is important to regularly consult a frequently-updated list such as <http://medicine.iupui.edu/clinpharm/ddis/table.aspx>; medical reference texts such as the Physicians' Desk Reference may also provide this information. As part of the enrollment/informed consent procedures, the participant will be counseled on the risk of interactions with other agents, and what to do if new medications need to be prescribed or if the participant is considering a new over-the-counter medicine or herbal product.

3.2.12 The participant has experienced any of the following:

- Clinically-significant gastrointestinal bleeding within 6 months before the first dose of study treatment
- Hemoptysis of  $\geq 0.5$  teaspoon (2.5 mL) of red blood within 3 months before the first dose of study treatment

- Any other signs indicative of pulmonary hemorrhage within 3 months before the first dose of study treatment

3.2.13 The participant has radiographic evidence of cavitating pulmonary lesion(s).

3.2.14 The participant has tumor invading or encasing any major blood vessels.

3.2.15 The participant has uncontrolled, significant intercurrent or recent illness including, but not limited to, the following conditions:

1. Cardiovascular disorders including:
  - a) Congestive heart failure (CHF): New York Heart Association (NYHA) Class III (moderate) or Class IV (severe) at the time of screening
  - b) Concurrent uncontrolled hypertension defined as sustained BP  $> 140$  mm Hg systolic, or  $> 90$  mm Hg diastolic despite optimal antihypertensive treatment within 7 days of the first dose of study treatment
  - c) Any history of congenital long QT syndrome
  - d) Any of the following within 6 months before the first dose of study treatment:
    - Unstable angina pectoris
    - Clinically-significant cardiac arrhythmias
    - Stroke (including TIA, or other ischemic event)
    - Myocardial infarction
    - Thromboembolic event requiring therapeutic anticoagulation (Note: participants with a venous filter (e.g. vena cava filter) are not eligible for this study)
2. Gastrointestinal disorders particularly those associated with a high risk of perforation or fistula formation including:
  - a) Any of the following within 28 days before the first dose of study treatment
    - Active peptic ulcer disease,
    - Inflammatory bowel disease (including ulcerative colitis and Crohn's disease), diverticulitis, cholecystitis, symptomatic cholangitis or appendicitis
    - Malabsorption syndrome
  - b) Any of the following within 6 months before the first dose of study treatment:
    - Abdominal fistula
    - Gastrointestinal perforation
    - Bowel obstruction or gastric outlet obstruction
    - Intra-abdominal abscess. Note: Complete resolution of an intra-abdominal abscess must be confirmed prior to initiating treatment with cabozantinib even if the abscess occurred more than 6 months before

the first dose of study treatment.

3. Other disorders associated with a high risk of fistula formation including PEG tube placement within 3 months before the first dose of study therapy.
4. Other clinically significant disorders such as:
  - a) Active infection requiring systemic treatment within 28 days before the first dose of study treatment. Participants with HIV infection will be eligible provided they meet the criteria specified in [Section 3.1.10](#). Participants with known Hepatitis B infection should be screened for active disease prior to study participation. Participants with known Hepatitis C infection must not be actively receiving treatment for the infection.
  - b) Serious non-healing wound/ulcer/bone fracture within 28 days before the first dose of study treatment
  - c) History of organ transplant
  - d) Concurrent uncompensated hypothyroidism or thyroid dysfunction within 7 days before the first dose of study treatment
  - e) History of major surgery as follows:
    - Major surgery within 3 months of the first dose of cabozantinib if there were no wound healing complications or within 6 months of the first dose of cabozantinib if there were wound complications.
    - Minor surgery within 1 months of the first dose of cabozantinib if there were no wound healing complications or within 3 months of the first dose of cabozantinib if there were wound complications.

In addition, complete wound healing from prior surgery must be confirmed at least 28 days before the first dose of cabozantinib irrespective of the time from surgery.

- 3.2.16 The participant is unable to swallow tablets that are whole (do not crush or chew or administer via NG-tube).
- 3.2.17 The participant has a corrected QT interval calculated by the Fridericia formula (QTcF)  $>500$  ms within 28 days before randomization. Note: If initial QTcF is found to be  $> 500$  ms, two additional ECGs separated by at least 3 minutes should be performed. If the average of these three consecutive results for QTcF is  $\leq 500$  ms, the participant meets eligibility in this regard.
- 3.2.18 History of allergic reactions attributed to compounds of similar chemical or biologic composition to cabozantinib (XL184).
- 3.2.19 Pregnant women are excluded from this study because cabozantinib (XL184) is a tyrosine kinase inhibitor with the potential for teratogenic or abortifacient effects. Because there is an unknown but potential risk for adverse events in nursing infants secondary to treatment of the mother with cabozantinib, breastfeeding should be discontinued if the mother is treated with cabozantinib.

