## PROTOCOL SYNOPSIS

**Title:** Phase I Trial of Cabozantinib (XL184) for Advanced Solid Tumors in Persons with HIV Infection

**Phase of Study:** Phase I

**Participating Institutions:** This protocol will be open to all AMC member sites.

**Accrual Target:** 16 to 42 participants

**Population:** Participants with incurable recurrent or metastatic solid tumors and HIV infection.

**Regimen:** This is a phase I, dose escalation study of cabozantinib (XL184) for advanced solid tumors in persons with HIV infection. Cabozantinib will be administered orally as a once daily dose continuously for 28-day cycles, according to the Protocol Schema. Participants will be stratified into three groups based on which HAART therapy they are receiving. The first group (**Stratum A**) will be participants on either ritonavir or cobicistat (potent CYP3A4 inhibitor)-containing antiretroviral therapy. Since a potential interaction leading to higher drug levels of cabozantinib in participants on ritonavir or cobicistat is expected, participants will be dose escalated, starting at ~33% of the standard dose (60 mg), using a classic 3 + 3 phase I clinical trial design. Dose increases will be in 20 mg increments to a maximum of 60 mg/day. The second group (**Stratum B**) will be participants being treated with either efavirenz or etravirine-containing regimens, in whom CYP3A4 induction may lead to lower levels of the study drug. These participants will be treated at the standard dose of cabozantinib, then dose escalated by 20 mg/cohort to a maximum of 100 mg/day in a 3 + 3 design. The third group (**Stratum C**) will include participants taking antiretrovirals not specified in Stratum A or B, or who are not receiving active antiretroviral therapy. These participants will be treated at the standard dose of 60 mg/day; no dose escalation is planned in this Stratum.

In this trial, a dose-limiting toxicity (DLT) will be defined as any cabozantinib-related grade 3 or 4 non-hematologic toxicity during the first cycle of therapy, including grade 3 nausea and/or vomiting and grade 3 diarrhea despite prophylaxis and/or treatment or any of the following grade 4 hematologic toxicities during the first cycle of therapy: thrombocytopenia, neutropenia of more than 5 days duration, and neutropenia of any duration with fever or documented infection; additionally, treatment delay of 14 days or greater during Cycle 1 due to unresolved toxicity or any

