## 5.0 TREATMENT PLAN

### 5.1 Agent Administration

Treatment will be administered on an outpatient basis. Reported adverse events and potential risks are described in [Section 7.0](#). Appropriate dose modifications are described in [Section 6.0](#). No investigational or commercial agents or therapies other than those described below may be administered with the intent to treat the participant's malignancy.

Cabozantinib will be administered orally as once daily doses continuously over 28 day cycles in each of three treatment strata in participant cohorts as detailed in the table below. The starting dose in each treatment Stratum will be Dose Level 1. Dose escalation will proceed in participant cohorts within each Stratum according to the scheme described in [Section 5.2](#).

**NOTES: The participant will be requested to maintain a medication diary of each dose of medication. The medication diary will be returned to clinic staff at the end of each course.**

**The site will be required to document study agent return by participant in source documents. Non-compliance with study agent administration should be noted at the time of diary collection and the participant should be instructed again regarding dosing instructions.**

**Missed cabozantinib doses will NOT be made up. Participants who have missed a dose should wait until the next scheduled dose to resume therapy.**

For Stratum A, one dose de-escalation cohort (Dose Level -1) will be permitted for excessive toxicity observed at the initial (Dose Level 1) cohort. For Stratum B and Stratum C, two dose de-escalation cohorts (up to Dose Level -2) will be permitted for toxicity observed at initial cohorts.

For participants treated on Stratum A no dose escalation will proceed beyond Dose Level 3 (60 mg). For participants treated on Stratum B, no dose escalation will proceed beyond Dose Level 2 (100 mg). For participants treated on Stratum C, no dose escalation will proceed beyond Dose Level 1.

Dose Escalation Schedule			
Dose Level	Dose of Cabozantinib (XL184)*		
	Stratum A ART Regimens Including Drugs that Inhibit CYP3A4 A (mg/day)	Stratum B ART Regimens Including Drugs that Induce CYP3A4 B (mg/day)	Stratum C All Other ART Regimens C (mg/day)
Level -2	-	20	20
Level -1	20 mg every other day	40	40
Level 1	20	60	60
Level 2	40	100	-
Level 3	60	-	-

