*\* Cabozantinib (XL184) must be taken whole and on an empty stomach. Participants must fast for 2 hours before and 1 hour following each dose of cabozantinib (XL184). To permit pharmacokinetic sampling studies, AM dosing is required during the first cycle of therapy.*

AStratum A: Participants taking either ritonavir-boosted or cobicistat-boosted ART regimens

BStratum B: Participants taking either efavirenz or etravirine-based ART regimens.

CStratum C: Participants taking any antiretrovirals not specified in Stratum A or B as of November 30, 2012, and participants who are not taking an ART regimen.

**Note: if an antiretroviral is FDA-approved after November 30, 2012, consult the Study Pharmacologist for Stratum designation).**

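### Permitted unboosted indinavir or nelfinavir falls into Stratum C at 60 mg, although the protocol classes both as strong CYP3A4 inhibitors; regimens that meet both the A and B rules also have no tie-break at entry

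*Combined protocol and SAP*

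**What the plan says.** **Who may enter.** Section 3.1.9 admits participants whatever their antiretroviral regimen. Section 3.2.11 excludes a list of CYP3A4 inhibitors but exempts antiretrovirals, including "protease inhibitors (ritonavir, indinavir, lopinavir/ritonavir, saquinavir, nelfinavir) is permitted". It adds that "ritonavir and cobicistat is permitted for participants considered for the CYP3A4-inhibitor based ART regimen arm (Stratum A) of the trial". Section 3.2.10 has the matching sentence for inducers: "Use of efavirenz or etravirine is permitted for participants considered for the CYP3A4-inducer based ART regimen arm (Stratum B) of the trial".

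**Which drugs are strong inhibitors.** Section 5.3.1.3, repeated in 8.1.1, names indinavir, nelfinavir and ritonavir in one list of strong CYP3A4 inhibitors. It then refers antiretroviral use back to 3.2.10 and 3.2.11.

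**Why Stratum A starts low.** The Synopsis gives the reason: "Since a potential interaction leading to higher drug levels of cabozantinib in participants on ritonavir or cobicistat is expected". The start is therefore about a third of the 60 mg standard dose.

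**How strata are assigned.** In the Section 5.1 dose table the Stratum A column is headed "ART Regimens Including Drugs that Inhibit CYP3A4", but footnote A narrows it to "Participants taking either ritonavir-boosted or cobicistat-boosted ART regimens". Footnote C takes the remainder: "Participants taking any antiretrovirals not specified in Stratum A or B as of November 30, 2012", plus participants on no antiretroviral regimen. Sections 12.1 and 12.3 assign strata in the same way, with no date limit on the Stratum C rule. One consultation step exists, for the case where an "antiretroviral is FDA-approved after November 30, 2012, consult the Study Pharmacologist for Stratum designation".

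**What follows from assignment.** Starting doses are 20 mg in A and 60 mg in B and C. Section 12.3 runs escalation and determines the MTD separately in each stratum.

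**The concern.** The protocol's reason for a 20 mg start is that a strong CYP3A4 inhibitor is expected to raise cabozantinib levels. Two permitted drugs that the protocol puts in the same class as ritonavir do not get that start. Their assignment is defined, but it sits badly with the stated reason and with the heading of the Stratum A column.

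Three things are at stake. First, a participant on one of these drugs receives 60 mg as a first dose with no step-up. Section 6.1.16 counts CYP3A4 inhibitors among the factors that may raise drug levels and contribute to QTc prolongation. Second, any DLT is charged to Stratum C, which is meant for regimens with neither the boosters nor the named inducers. Section 12.2 expects 6 participants there, and under Section 5.2 a second DLT at a dose level means the MTD has been exceeded, so one such participant could supply half of that count. Third, the Stratum C PK summary would mix inhibited and uninhibited participants, which weakens the drug-interaction objective in 1.2.1.

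The lesser issue is overlap. Stratum A is defined by containing ritonavir or cobicistat, and Stratum B by containing efavirenz or etravirine. Neither definition excludes the other.

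**Working it through.** **Plan's own figure.** Stratum A start over standard dose: 20/60 = 33.3%, which agrees with the Synopsis (about 33%).

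**Rule check by regimen type** (footnotes in 5.1; 12.1; 12.3)
- Ritonavir- or cobicistat-boosted, no efavirenz or etravirine: meets A only, start 20 mg.
- Efavirenz or etravirine, no booster: meets B only, start 60 mg.
- Unboosted indinavir or nelfinavir, no efavirenz or etravirine: meets neither A nor B, so C, start 60 mg. The documents do not give approval dates. I assume both drugs were approved by November 30, 2012, so the consultation note does not reach them.
- Booster plus efavirenz or etravirine: meets both A and B, start 20 or 60 mg, a ratio of 60/20 = 3. No entry rule chooses between them.

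Saquinavir and delavirdine are also permitted by 3.2.11, but 5.3.1.3 does not name them as strong inhibitors, so the point is confined to indinavir and nelfinavir.

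**Participants cleared before 60 mg** (escalation table, 5.2). In Stratum A, the 20 and 40 mg levels must each clear with 0 DLTs in 3 or 1 in 6.
- Minimum: 3 + 3 = 6.
- With one DLT at each level: 6 + 6 = 12.
- In Stratum C, 60 mg is Level 1, so none.

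**Size of the exposure effect.** Inputs: AUC +38% with ketoconazole and −77% with rifampin (5.3.1.3); MTD of about 138 mg freebase (2.4). Assumptions: ketoconazole stands in for indinavir or nelfinavir, and AUC is proportional to dose. Equivalent dose = dose × AUC ratio.
- Stratum C start: 60 × 1.38 = 82.8 mg; 82.8/138 = 60% of that MTD.
- Stratum A start: 20 × 1.38 = 27.6 mg; 27.6/138 = 20%.
- The 138 mg figure is a capsule result, and this trial uses tablets. Section 2.4 reports tablet AUC 15% to 19% higher, with no statistical difference shown. Applying it gives 60% × 1.15 = 69% to 60% × 1.19 = 71%, still below the MTD.

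**Booster plus inducer.** The documents give no net effect. Taking the two single-drug results as the range, the multiplier lies between 1 − 0.77 = 0.23 and 1.38.
- At 20 mg: 20 × 0.23 = 4.6 mg to 27.6 mg equivalent.
- At 60 mg: 60 × 0.23 = 13.8 mg to 82.8 mg equivalent.

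**The case against.** The Stratum A definition is applied consistently throughout, and the Synopsis gives its reason only for ritonavir and cobicistat. The column heading is qualified by its own footnote, and 5.3.1.3 is a general interaction list that defers to the eligibility criteria. That is a fair account of what the rule is. It does not explain why a strong-inhibitor user needs a stepped start in one stratum and none in another.

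The safety argument against the concern is stronger, and much of it stands. The standard dose is 60 mg and there is prior clinical experience (1003 patients in Section 2.4), so the absence of a step-up in C is not an absence of experience. The equivalent dose stays below the previously determined MTD. Cycle 1 has weekly visits and ECGs, and dose reduction is allowed. PK is sampled in all participants, and Section 10.1.1 compares parameters across antiretroviral therapies, so a careful analyst could separate these participants. None of this corrects whose DLTs count toward which stratum.

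A reader might infer from the bilirubin allowance in 3.1.6 that unboosted indinavir use was expected. The text does not say unboosted, and boosted indinavir would go to A. The documents show only that such use is permitted.

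A reader might also infer that the A/B overlap contradicts the CYP3A4 rationale, or that sites will in fact start the same regimen at different doses. It is a missing tie-break. Section 3.2.11 ties boosters to A, and 5.3.1.2 and 5.4 remove a participant from another stratum who later changes to a booster. Those texts lean toward A but do not govern entry, and 3.2.10 has parallel wording for B. The enrollment checklist, which might settle the matter, is not in the documents.

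**Conclusion.** The main point holds. A stated rule, not a missing one, sends permitted unboosted indinavir or nelfinavir to Stratum C at 60 mg, three times the start that the protocol chose for ritonavir and cobicistat users on grounds of inhibition. The result is a first dose with none of A's 6 to 12 participants of step-up, and some contamination of C's DLT count and PK summary.

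The expected safety effect is modest: about 83 mg equivalent, roughly 60% of the previously determined MTD, or about 70% if the tablet difference is applied. This rests on ketoconazole as a proxy and on dose-proportional AUC. The number of participants affected is not given and may be small.

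The A/B overlap is real but carries less weight. A reader might infer that a dual regimen entered in Stratum B would reach the MTD at the 100 mg level (100 × 1.38 = 138 mg). That would require the inducer to have no effect, and nothing in the documents supports that.

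The wording should be corrected, but the documents do not show that participants would be dosed above the previously determined MTD.

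**What to change.** In the stratum footnotes and in 12.1 and 12.3, extend the Study Pharmacologist consultation, now limited to newly approved antiretrovirals, to two further cases:

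- regimens with a strong CYP3A4-inhibiting antiretroviral that is not ritonavir- or cobicistat-boosted (indinavir, nelfinavir), so that they do not default to C at 60 mg;
- regimens that meet both the A and B definitions.

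The second case should not be fixed at Stratum A by rule. The net effect of a booster plus an inducer is not given, and 20 mg could act like as little as 4.6 mg. Section 6.0 bars intra-participant escalation, so a participant could stay underdosed. Lower-exposure participants counted in A's cohorts of 3 to 6 could also push A's MTD upward for those on an inhibitor alone.

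The cost is a few sentences of amendment and an occasional consultation before enrollment. No new data are needed, because Section 9.1.1 already records the antiretroviral regimen for the 4 weeks before enrollment.
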